## 2. SUMMARY

### Type of request

Phase II clinical trial of oral sodium chloride in a new indication.

### Sponsor

The Foundation for Biomedical Research of the Hospital Universitario Ramón y Cajal (FIBioHRC)

### Funder

The Spanish Health Ministry through the Fondo de Investigaciones Sanitarias (FIS) of the Instituto de Salud Carlos III, Madrid.

### Clinical trial title

Efficacy of oral and intravenous sodium chloride administration in the prophylaxis of post-contrast acute kidney injury in outpatients (PNIC-Na).

### Protocol code

EudraCT: 2013-001229-15

### Clinical Research Ethics Committee that evaluates the trial

Clinical Research Ethics Committee from Hospital Universitario Ramón y Cajal

### Experimental and control group

Experimental group: 500 mg capsules of sodium chloride (NaCl), supplied by the Pharmacy Department of the Hospital Universitario Ramón y Cajal. The total dose administered will be 100 mg/kg of body weight distributed in 60 hours, 48 hours before and 12 hours after the procedure. Appendix C describes the specific regimen according to weight.

Control group: 0.9% NaCl solution, supplied by the Pharmacy Department of the Hospital Universitario Ramón y Cajal. Dose: 3 ml/kg in the hour prior to the procedure and 2 ml/kg/hour in the following 4 hours.

### Clinical trial phase

Phase II.

### Main objective

To compare the incidence of post-contrast acute kidney injury (PC-AKI) in high-risk ambulatory patients after oral versus intravenous administration of sodium chloride prophylaxis.

### **Design**

Phase 2, monocenter, randomized, open-label, controlled clinical trial for non-inferiority.

### **Disease or condition studied**

Post-contrast acute kidney injury.

### **Main outcome**

The main efficacy criteria for PC-AKI is defined as an increase in serum creatinine  $> 0.3$  mg/dL or a reduction  $>25\%$  in estimated glomerular filtration rate (MDRD-4), within 48 hours from baseline.

### **Study population**

Patients at high risk of developing PC-AKI. The total number of patients will be 266, 133 for each treatment group.

### **Study duration**

Three years.

### **Schedule and expected completion date**

After approval by the Ethics Committee and other regulatory bodies:

Patient inclusion: 30 months.

Duration of treatment and follow-up: 72 hours.

Overall estimated completion of the study 36 months after approval.

## 4. RATIONALE AND OBJECTIVES

### 4.1. Background and current status

Post-contrast acute kidney injury (PC-AKI) is defined by an increase in plasma creatinine greater than 0.3 mg/dL, or greater than 25-50% of the baseline value, 24-48 hours after administration in the absence of other causes (surgery, arteriothrombotic disease, nephrotoxic, hemodynamically compromised or hypovolemia). Despite it is usually transitory, it is a relevant complication. This is the third most frequent cause of acute renal failure in hospitalized patients, with an incidence of around 12%. It may require permanent dialysis and is associated with an increased risk of other non-renal complications. It also increases hospitalization time and mortality. Up to 30% of subjects who suffer PC-AKI will remain with some degree of renal failure.

The existence of previous renal failure, diabetes, heart failure and the type and volume of contrast used have been recognized as risk factors. The incidence of PC-AKI in general population is low (0.6-2.3%), increases in elderly and diabetic patients (5-29%), and is very striking in the presence of renal failure (incidence 15-55%). Predictive scales have been developed for early identification of those at risk in whom preventive measures are especially indicated. The European Society of Urogenital Radiology established a Contrast Safety Committee in 1996, which recommends the measurement of renal function prior to the test, and after it within a maximum of 7 days, as well as preventing measures in patients considered to be at risk. Regarding the assessment of renal function, it is advisable to estimate the glomerular filtration rate using formula such as the Modification of Diet in Renal Disease (MDRD). However, the MDRD formula may underestimate glomerular filtration rate in healthy subjects and overestimate it in diabetic patients with normal plasma creatinine. Cystatin C is a low molecular weight protein freely filtered and metabolized after its reabsorption in the proximal tubule and its values show less variability than those of creatinin.

Different in vitro and animal studies suggest that PC-AKI is a consequence of the existence of both direct and indirect tubular damage triggered by ischemia secondary to reactive oxygen species that induce local vasoconstriction. On the other hand, the presence of contrast in the renal tubular lumen constitutes an osmotic force that induces natriuresis and stimulates tubule-glomerular feedback with reduction of renal perfusion. These evidences constitute the pathophysiological basis for the benefit of hydration in patients submitted to contrast administration.

Numerous studies on PC-AKI prophylaxis have been performed but there is still not enough evidence to establish a clear recommendation. In addition to the use of hypo or isomolar contrast agents, experts advise the administration of intravenous isotonic solutions, with a wide variability between the type of solution and its administration schedule. Current recommendations are intravenous volume expansion, which is inapplicable in most outpatients undergoing radiological procedures.

Most of the preventive guidelines evaluated have used intravenous saline or sodium bicarbonate solutions. It has been postulated that sodium bicarbonate offers greater protection than sodium chloride probably because of its urinary alkalinizing effect. However, clinical trials and several recent meta-analyses have not demonstrated a greater efficacy of sodium bicarbonate vs sodium chloride (NaCl) in the prevention of PC-AKI. A clinical trial is currently underway to conclusively clarify the efficacy of bicarbonate versus sodium chloride infusion (ClinicalTrials.gov NCT00930436).

N-acetyl-cysteine has been used in PC-AKI prophylaxis with heterogeneous results. Recently, a clinical trial with a large number of patients has shown no benefit associated with the use of N-acetyl-cysteine, so its administration should probably be abandoned.

Regarding oral volume expansion, studies are scarce, with non-comparable designs, limited statistical power and heterogeneous results. The findings of a recent study with NaCl suggest that oral administration is non-inferior to intravenous administration in the prevention of PC-AKI in high-risk subjects. Nevertheless, due to the small number of patients in each group no conclusions can be drawn.

An important aspect of PC-AKI is the early detection, before the loss of renal function occurs. In this sense, creatinine is not a good marker, since its elevation occurs when there is an established renal failure. Sensitive biomarkers of renal damage would allow not only to an early detection of renal injury, but also the identification of those patients at risk of suffering it. Among the new candidate predictors of early kidney injury is the measurement in urine of neutrophil gelatinase-associated lipocalin (NGAL), an enzyme released after renal tissue injury, which is one of the most accurate, sensitive and specific methods. Other state-of-the-art urinary markers related to the early diagnosis of renal damage are renal damage molecule 1, N-acetyl glucosaminidase, and other molecules patented by Spanish researchers: t-gelsolin (a proteolytic fragment of gelsolin) and ganglioside M2 activating protein (GM2AP).

On the basis of the above, and taking into account the prevalence and clinical relevance of this complication, the possibility of introducing an effective oral regimen for the prevention of PC-AKI would have a considerable impact, both in terms of patient benefit and health care cost. Otherwise, the patient would have to be hospitalized. We consider the project to be sufficiently justified due to the high incidence of PC-AKI. The selected population group presents a high risk, so the expected benefit of this study will be especially relevant in this population. On the other hand, the incorporation of biomarkers of early diagnostic and/or prognostic utility would be of great help in identifying those patients at greater risk of suffering a severe nephropathy.

#### **4.2. Benefits and risks for humans**

The intended benefit is the demonstration that oral NaCl is non-inferior to an intravenous administration. This would allow the widespread application of a preventive treatment for contrast nephropathy, easy to administer to all patients. Likewise, the study could help us to identify patients at risk of PC-AKI analyzing the molecules mentioned.

The administration of saline compounds can increase blood volume and increase congestive symptoms such as edema. However, at the doses used and taking into account the criteria required for participation, patients are not expected to suffer any complication from the study. In any case, oral treatment, which is the subject of the study, should not produce more volume overload at the proposed doses than conventional intravenous treatment.

#### **4.3. Justification of the route of administration, dose, regimen and treatment period**

The proposed intravenous regimen of 11 mL/kg body weight of 0.9% NaCl, over the course of 6 hours is within the accepted recommendations. The oral regimen is intended to provide volume support with NaCl for a reasonable period of 60 hours.

#### **4.5. Description of the study groups**

##### **Experimental group**

Sodium chloride capsules of 500 mg, supplied by the Pharmacy Department of the hospital. The total dose administered will be 100 mg/kg distributed in 60 hours, 48 hours before and 12 hours after the procedure. Water (250 mL) will be administered with each oral dose, ensuring a minimum daily water intake of 750 mL.

##### **Control group**

Sodium chloride solution 0.9% will be supplied by the Pharmacy Department of the hospital at a dose of 3 mL/kg in the hour before to the procedure and 2 mL/kg/hour in the 4 hours after.

#### **4.6. Description of the study population**

The study will be performed in 266 outpatients aged over 65 years, with prior consent, at high risk of developing PC-AKI undergoing a contrast-enhanced CT scan (CE-CT). The following risk factors were considered: diabetes mellitus, stable heart failure and renal insufficiency (estimated glomerular filtration rate calculated by the MDRD-4 formula between 30 and 59 mL/min).

In order to ensure that the amount, volume and type of contrast infusion is similar in all subjects, only patients who underwent CE-CT were selected.

#### **4.7. Main objective**

To compare the incidence of PC-AKI after oral vs. intravenous administration of NaCl in high-risk outpatients.

#### **4.8. Secondary objectives**

- To study and evaluate the clinical usefulness of various biomarkers of damage in PC-AKI, both for early diagnosis of renal damage and for prior stratification of the risk of PC-AKI.
- To elaborate a recommendation applicable to elderly outpatients at high risk of developing PC-AKI.

## 5. TRIAL TYPE AND DESIGN

### 5.1. Clinical trial phase

Clinical trial phase 2.

### 5.2. Main and secondary variables

#### Primary endpoint

PC-AKI is defined by the presence any of the following criteria in the first 48 hours after contrast administration.

- Increase in serum creatinine greater than 0.3 mg/dL from baseline.
- Reduction in glomerular filtration rate estimated by the MDRD\* formula greater than 25% from baseline.

\*MDRD:  $186 \times (\text{Cr}) - (1.154) \times (\text{Age}) - (0.203) \times 0.742$  (if female)  $\times 21$  (if African American).

#### Clinical variables

The following variables will be collected between 7 days and 24 hours before contrast administration:

- General data: patient code and date of inclusion.
- Demographic data: date of birth and gender.
- Personal history: smoking, hypertension, diabetes mellitus, heart failure, dyslipidemia, ischemic heart disease, atrial fibrillation, chronic kidney disease, peripheral arterial disease, cerebrovascular disease, anemia, COPD, hypoventilation ( $\text{pCO}_2 > 50 \text{ mmHg}$ ).
- Anamnesis and physical examination: NYHA functional class orthopnea, edema in extremities, ischemic chest pain, height, weight, BMI, HR, blood pressure. Pulmonary auscultation, hepatomegaly.
- Other analytical determinations: hemoglobin, basal glycemia, glycosylated hemoglobin, oxygen saturation by pulse oximetry, BNP.
- Imaging tests: electrocardiogram.
- Concomitant medication.
- Procedure data: volume of contrast administered.

#### Biological variables

Apart from creatinine measurement and glomerular filtration rate according to MDRD, which constitutes the primary response variable of the study, the following parameters will be measured immediately before the procedure, and at 24 and 48 hours after contrast administration: plasma cystatin C, serum biochemistry with ions, venous gasometry, urinary concentrations of: NGAL, KIM-1\*, NAG\*, t-gelsolin\*, GM2AP\*, sodium, microalbuminuria and protein.

\* The biomarkers identified with an asterisk will be stored at -80 °C until processing in the Laboratory of the Heart Failure and Vascular Risk Unit of the Internal Medicine Department of Hospital Universitario Ramón y Cajal. This Unit guarantee traceability, quality and safety in computer management, storage control and processing samples.

### **5.3. Study design**

PNIC-Na is a phase 2, monocenter, randomized, open-label, non-inferiority trial. Two types of preventive treatment will be compared in patients undergoing a CE-CT scan:

- Oral prophylaxis with NaCl capsules and free water intake (250 mL of water with each capsule, ensuring a water intake of 750 mL/day) in the 48 hours prior to contrast exposure (n=133). It will be performed on an outpatient basis at a dose of 100 mg/kg body weight distributed in 60 hours, 48 hours prior to the procedure and 12 hours after. Appendix C describes the specific dose according to weight.
- Intravenous prophylaxis with 0.9% NaCl before and after contrast exposure (n=133). It will consist of in-hospital administration of 3 mL/kg in the hour before and 2 mL/kg in the 4 hours after the procedure.

The contrast used will be iodixanol (320 mg iodine/mL, infusion rate 2-5 mL/sec).

The corresponding treatment will be administered after medical prescription, validation by the pharmacist and confirmation. The nurse in charge of the patient will administer the treatment. The intravenous prophylaxis schedule for the study will begin in the Radiology Department of the Hospital, and will conclude in the Clinical Trials Unit of the same center.

The study will consist on the schedule of visits described in section 9.2.

### **5.4. Recruitment and randomization**

Patients will be recruited from the Heart Failure and Vascular Risk Unit (UICARV) of the Internal Medicine Department of the Hospital Universitario Ramón y Cajal. Eligible patients will be informed at the time of requesting the contrast-enhanced CT scan and, after signing the consent, they will be selected. They may also be identified from the requests made to the Radiology department. In this case, the patient will be contacted prior to get the informed consent. After their definitive inclusion they will be randomized to one of the two arms. A 1:1 randomization will be performed. The randomization sequence will be generated by computer in variable blocks, ranging from 4 to 6. An automated allocation system will be used, so that the allocation sequence will be unknown to the researchers participating in the study. The patient will be considered as randomized as soon as a randomization number is assigned.

### **5.5. Treatment**

#### **Treatment under study**

Oral prophylaxis with NaCl capsules and free water intake (250 mL of water with each capsule, ensuring a water intake of 750 mL/day) in the 48 hours prior to contrast exposure (n=133). It will be performed on an outpatient basis at a dose of 100 mg/kg body weight distributed in 60 hours, 48 hours prior to the procedure and 12 hours after. Appendix C describes the specific dose according to weight. Common salt will be used

in the experimental group. It will be encapsulated in the Pharmacy Department to ensure the exact dose administered to each subject in the trial.

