# **6. SELECTION AND WITHDRAWAL OF SUBJECTS**

## **6.1. Inclusion criteria**

Patients are eligible to be included if they meet the following inclusion criteria: outpatients, aged over 65 years old, undergoing a contrast-enhanced CT scan, who are at high risk of developing PC-AKI, defined as having at least one of the following risk factors: diabetes mellitus, stable heart failure, chronic kidney disease (MDRD-4 between 30 and 59 mL/min), and capable of giving signed informed consent.

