## **6.2. Exclusion criteria**

- Glomerular filtration rate less than 30 mL/min.
- Presence of hypokalemia (serum potassium less than 3.5 mEq/L).
- Performance of other procedures with intravenous contrast in the previous fifteen days.
- Administration of nephrotoxic drugs (NSAIDs, aminoglycosides and/or potentially nephrotoxic chemotherapy) in the last 72 hours, or anticipation of receiving them in the following hours.
- Chronic decompensated pathology: acute heart failure, decompensated COPD or poorly controlled arterial hypertension.
- Allergy to iodinated contrasts.
- Patients diagnosed with hyperchloraemia or hypernatremia.
- When assessing the inclusion of a patient in the study, all the specifications of the technical data sheet in relation to "special warnings and precautions for use" will be taken into account.

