### Concomitant treatments

**Permitted:** Diuretic and hypotensive medication will be maintained, as long as there have been no changes in the previous 10 days. No changes in these medications will be allowed, except in special cases, during the 48 hours following the CE-CT. Those patients in treatment with metformin, will suspend this medication from 48 hours before to 24 hours after the administration of the contrast, and it can be replaced by the introduction or temporary increase of insulin. During the 48 hours before and 24 hours after the procedure, free water and salt intake will be allowed.

**Prohibited:** Any nephrotoxic agent will be prohibited (NSAIDs, chemotherapy or immunosuppressants, nephrotoxic antibiotics) during the 10 days before and 48 hours after the procedure.

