**APPENDIX C. SODIUM CHLORIDE ADMINISTRATION SCHEDULE ACCORDING TO WEIGHT**

With each oral dose, 250 mL of water should be administered, ensuring a minimum daily intake of 750 ml of water.

WEIGHT (Kg) and total dose	IV ADMINISTRATION (NaCl 0.9%)	ORAL ADMINISTRATION (NaCl capsules 500 mg)*	
50 - <55	550 mL	5 g (10 capsules)	
85 mEq	1 hour pre-test 150 mL 0-4 hours post-test 400 mL	48 hours pre-test 1 capsule 40 hours pre-test 1 capsule 32 hours pre-test 1 capsule 24 hours pre-test 1 capsule 16 hours pre-test 1 capsule 8 hours pre-test 2 capsules 0 hours 2 capsules 12 hours post-test 1 capsule	
55 - <60	605 mL	5.5 g (11 capsules)	
93,5 mEq	1 hour pre-test 165 mL 0-4 hours post-test 440 mL	48 hours pre-test 1 capsule 40 hours pre-test 1 capsule 32 hours pre-test 1 capsule 24 hours pre-test 1 capsule 16 hours pre-test 2 capsules 8 hours pre-test 2 capsules 0 hours 2 capsules 12 hours post-test 1 capsule	
60 - <65	660 mL	6 g (12 capsules)	
102 mEq	1 hour pre-test 180 mL 0-4 hours post-test 480 mL	48 hours pre-test 1 capsules 40 hours pre-test 1 capsules 32 hours pre-test 1 capsules 24 hours pre-test 2 capsules	

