**PNIC-Na Protocol**

Date & Version No: 02-Aug-2013 V2.0 (ENG)

	0-4 hours post-test 760 mL	40 hours pre-test 2 capsules 32 hours pre-test 2 capsules 24 hours pre-test 2 capsules 16 hours pre-test 3 capsules 8 hours pre-test 3 capsules 0 hours 3 capsules 12 hours post-test 2 capsules
>100  177 mEq	1100 mL  1 hour pre-test 300 mL 0-4 hours post-test 800 mL	10 g (20 capsules)  48 hours pre-test 2 capsules 40 hours pre-test 2 capsules 32 hours pre-test 2 capsules 24 hours pre-test 3 capsules 16 hours pre-test 3 capsules 8 hours pre-test 3 capsules 0 hours 3 capsules 12 hours post-test 2 capsules

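### Sections 5.3 and 5.5 attach 250 mL of water to each capsule, while 4.5 and Appendix C attach it to each oral dose: a minor but real contradiction in the oral regimen

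*Combined protocol and SAP*

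**What the plan says.** The accompanying water is described in four places in the current text, under two different rules.

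- **Per capsule.** Section 5.3 (Study design) and section 5.5 (Treatment under study) both say "250 mL of water with each capsule, ensuring a water intake of 750 mL/day". Both apply this to the 48 hours before contrast, mention free water intake, and refer to Appendix C for the dose by weight.
- **Per dose.** Section 4.5 (Experimental group) says "Water (250 mL) will be administered with each oral dose, ensuring a minimum daily water intake of 750 mL". Appendix C opens with the same rule: "With each oral dose, 250 mL of water should be administered, ensuring a minimum daily intake of 750 ml of water".

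Appendix C then lists capsules by time for 11 weight bands, with six pre-test times (48, 40, 32, 24, 16 and 8 hours), one at 0 hours and one at 12 hours post-test. The number of capsules per time varies from 1 to 3. In the heaviest band, for example, the second pre-test day reads "24 hours pre-test 3 capsules 16 hours pre-test 3 capsules 8 hours pre-test 3 capsules".

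Three other provisions bear on the point. Section 7.1 (Concomitant treatments) states: "During the 48 hours before and 24 hours after the procedure, free water and salt intake will be allowed". The qualifying risk factors in 6.1 are "diabetes mellitus, stable heart failure, chronic kidney disease", in outpatients over 65. Section 6.2 excludes "Chronic decompensated pathology: acute heart failure, decompensated COPD or poorly controlled arterial hypertension". No section says which water rule governs.

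**The concern.** A capsule and a dose are not the same unit in this trial. If every dosing time had one capsule, the two wordings would agree. Since most times have two or three, someone who follows 5.5 literally would instruct a patient to drink more than someone who follows Appendix C, and the gap grows with body weight.

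The water is described as part of the oral regimen in 4.5, 5.3 and 5.5, so the plan should state one volume. The patients take the capsules at home. They are over 65, some with stable heart failure, and section 4.2 itself names congestive symptoms as the risk of saline compounds. The adherence check in 5.8 and 7.2 counts capsules and returned blisters. No section describes recording water intake, so a mix of the two rules across patients would not show in the data that the plan collects.

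**Working it through.** **Inputs.** 250 mL per unit (4.5, 5.3, 5.5, Appendix C); daily figure 750 mL (the same four places); capsules per dosing time (Appendix C). The window is the 48 hours before contrast, that is, the six doses from 48 to 8 hours pre-test. The 0-hour dose is left out here and added as a check below.

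**Reproducing the plan's daily figure.** Pre-test dosing is every 8 hours, so there are 3 doses per day. Per dose: 3 × 250 = 750 mL/day, which is the stated figure. Per capsule, the 48-hour average runs from 7 × 250 / 2 = 875 mL/day to 15 × 250 / 2 = 1875 mL/day, so no band gives 750 mL/day over the 48 hours.

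**Prescribed accompanying water, six pre-test doses.** Per dose: 6 × 250 = 1500 mL in every band. Per capsule: pre-test capsules × 250 mL.

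| Weight (kg) | Pre-test capsules | Per capsule (mL) | Excess over 1500 mL | Ratio |
|---|---|---|---|---|
| 50-<55 | 7 | 1750 | 250 | 1.17 |
| 55-<60 | 8 | 2000 | 500 | 1.33 |
| 60-<65 | 9 | 2250 | 750 | 1.50 |
| 65-<70 | 10 | 2500 | 1000 | 1.67 |
| 70-<75 | 11 | 2750 | 1250 | 1.83 |
| 75-<80 | 11 | 2750 | 1250 | 1.83 |
| 80-<85 | 12 | 3000 | 1500 | 2.00 |
| 85-<90 | 13 | 3250 | 1750 | 2.17 |
| 90-<95 | 13 | 3250 | 1750 | 2.17 |
| 95-<100 | 14 | 3500 | 2000 | 2.33 |
| >100 | 15 | 3750 | 2250 | 2.50 |

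The ratio is at least 2 in the five bands from 80 kg. It reaches 2.5 only above 100 kg.

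**By day.** Per capsule, the first pre-test day (48, 40 and 32 hours) gives 750 to 1500 mL and the second (24, 16 and 8 hours) gives 1000 to 2250 mL. Neither falls below 750 mL in any band.

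**Sensitivity to the window.** Counting the 0-hour dose gives 2250 to 4500 mL per capsule against 7 × 250 = 1750 mL per dose. The whole 60-hour course gives 2500 to 5000 mL (10 to 20 capsules) against 8 × 250 = 2000 mL. The choice of window changes the figures but not the conclusion.

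**The case against.** The strongest reply is that the intent is clear. The 750 mL/day figure appears in all four places, and over the 48 hours only the per-dose rule produces it. The per-dose sentence heads the hour-by-hour schedule to which 5.3 and 5.5 send the reader, and those two sections carry the same sentence, which looks like one slip copied once. This stands as a strong inference. It does not remove the contradiction, because 5.3 and 5.5 cite Appendix C for the dose and not for the water.

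It is also fair to say that neither rule fixes the volume drunk. Free water is allowed, and 4.5 and Appendix C make 750 mL a minimum. This too stands, and it limits the point to prescribed accompanying water.

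Four stronger readings are tempting, and the documents do not support them.

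- *Patients would drink litres more, with a risk of overload.* The therapeutic information given at Visit 1 is not in the documents, so which rule patients are told is unknown. No difference in actual intake is shown, and acute heart failure is excluded.
- *The sentence in 5.3 and 5.5 contradicts itself.* Read as a floor, 750 mL/day is met on each pre-test day under the per-capsule rule as well.
- *The stated rationale makes the water volume central.* Section 4.3 says "The oral regimen is intended to provide volume support with NaCl for a reasonable period of 60 hours". That is support with NaCl and it does not mention water. The definition of Treatment A in 7.1 does not mention water either.
- *The rule falls short after the test, where the doses at 0 and 12 hours give only 500 mL.* The sentences in 5.3 and 5.5 cover only the 48 hours before contrast. The wording that does extend beyond the test, in 4.5 and Appendix C, already calls 750 mL a minimum.

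**Conclusion.** The contradiction is in the current treatment text and the arithmetic is exact. Following 5.3 or 5.5 literally prescribes 250 to 2250 mL more accompanying water over the six pre-test doses than 4.5 and Appendix C do, depending on weight. The figures rest on the Appendix C schedule as printed and on leaving out the 0-hour dose. That the per-dose rule is the intended one is an inference from the 750 mL/day figure and from the place of that rule at the head of the dosing schedule. The inference is close to certain, but no section states it.

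The impact is minor. The figures are prescribed water, not total intake. NaCl dose and timing, the capsule-based adherence check, the endpoint, the 5% margin and the sample size of 266 do not depend on it. It is worth correcting because it concerns what outpatients are told to take, and because the correction is nearly free.

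**What to change.** In sections 5.3 and 5.5, attach the 250 mL of water to each oral dose instead of each capsule. Use the opening sentence of Appendix C word for word in the instructions that patients in the oral arm receive at Visit 1.

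Optionally, call the 750 mL/day in 5.3 and 5.5 a minimum. This only brings the two sections into line with 4.5 and Appendix C.

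Cost: one phrase in each of two sentences, or two with the optional change, made through the amendment route in 14.5. No procedures, visits or patients are added.
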